#### Hearing Implant

- Does the subject have and audiological implant (Never implanted/Implanted, still in use/Implanted, not in use/Explanted)
- Does the subject have and audiological implant (Never implanted/Implanted, still in use/Implanted, not in use/Explanted) on test side
- Does the subject have and audiological implant (Never implanted/Implanted, still in use/Implanted, not in use/Explanted) on non-test side
- Does the subject have and audiological implant (Never implanted/Implanted, still in use/Implanted, not in use/Explanted) on both test side and non-test side

All information collected in the eCRF regarding hearing aid and hearing implant will be listed.

### 3.4.4.6 Audiogram

A descriptive presentation of audiograms at Screening will be presented (tabulated and graphically) as described in paragraph 3.7 by frequency (and Pure Tone Average (PTA4) for CHL and MHL (*mean of 500, 1000, 2000 and 4000Hz*) and for SSD (*mean of 500, 1000, 2000 and 3000Hz*)), test side, air/bone and masked/unmasked.

### 3.4.4.7 Soft tissue thickness

A descriptive presentation of Soft tissue thickness will be presented as described in paragraph 3.7.

### 3.4.4.8 Surgery

A descriptive presentation of surgery data will be presented as described in paragraph 3.7:

- Treatment ear (indicate left or right or both. In case of both, indicate “test ear”).
- Soft tissue thickness (mm)
- Type of anesthesia (general/local)
- Bone polishing/removal at the actuator site (yes/no)
- BI300 Implant length (3mm/4mm)
- Location of BI300 Implant (mm)
- Soft tissue reduction (yes/no)
- Surgical incision type (examples; C-shaped/S-shaped/straight)
- Location of the surgical incision in relation to the actuator (anterior/posterior)
- Estimated length of the surgical incision (mm)
- Placement of the coil
  - periosteal pocket (under periosteal)
  - on top of periosteum
  - on top of muscle
- Surgery time (time between first incision to last suture)

### 3.4.4.9 Usability

A descriptive presentation of surgery data by visit will be presented as described in paragraph 3.7:

- Magnet choice
- Sound Processor retention
- Sound Processor wearing comfort
- Use of SoftWear pad
- Daily use
- Daily streaming
- Battery lifetime
  - Did the “low battery” signal occur (yes/no)

### 3.4.4.10 BC Direct

A descriptive presentation of surgery data by visit will be presented as described in paragraph 3.7:

- BC Direct [0.25, 0.5, 0.75, 1.0, 1.5, 2.0, 3.0, 4.0 and 6.0 kHz] will be performed using a Baha Softband (preoperatively) at screening/baseline and using the Investigational device at fitting, 3- and 6-months post-surgery.

#### **3.4.4.11 Preoperative hearing aid**

The difference in hearing performance at fitting- 3- and 6 months post-surgery when using the Investigational device compared to a preoperative hearing aid (if used by the patient) assessed as:

- The difference in Adaptive speech in noise [signal-to-noise ratio, 50% speech understanding].

#### **3.4.4.12 Coil-to-coil measurement**

DLC measurements through-out the study will be presented.

#### **3.4.4.13 Implant site evaluation (numbness)**

Implant site evaluation (numbness) will be summarised by frequency and percent of:

1. No numbness,
2. Numbness over the implant Magnet Assembly area and
3. Numbness over the implant Magnet Assembly area and 2 cm outside the implant Magnet Assembly area by visit.

#### **3.4.4.14 Adverse events**

Separate tabulations of AEs, ADEs, SAEs, SADEs and AESIs will be produced. AEs, ADEs and AESIs will also be produced by severity (mild, moderate or severe) and relationship (related defined as Possibly, Probably and Definitely related). Number of events, number of subject and percent with events by System Organ Class (SOC, CTCAE) and CTCAE term will be presented.

#### **3.4.4.15 Device deficiency**

DDs will be reported by visit as described in paragraph 3.7.

#### **3.4.4.16 Concomitant medication**

Concomitant medications will be defined as start or end date from surgery to end of study and will be presented by listings.

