7.2.2 Exclusion Criteria

Subjects who meet any of the exclusion criteria described below will not be eligible for this clinical investigation.

1. Uncontrolled diabetes as judged by the investigator.
2. Condition that could jeopardise osseointegration and/or wound healing (e.g. osteoporosis, psoriasis, long-term systemic use of corticosteroids) or condition that may have an impact on the outcome of the investigation as judged by the investigator.
3. Insufficient bone quality and quantity to support successful implant placement.
4. Previous surgery and/or implantation with any bone conduction/active device on the side to be implanted, which jeopardize the implantation and use of the Osia 2 system, as judged by the investigator.
5. Use of ototoxic drugs that could be harmful to the hearing, as judged by the investigator.
6. Unable to follow investigational procedures, e.g. to complete quality of life scales, or unwilling to comply with the requirements of the clinical study as determined by the Investigator.
7. Condition with a likely negative progression and/or with expected relapses jeopardising general wellbeing and health-related quality of life as judged by the investigator.
8. Subject that has received radiotherapy in the area of implantation or is planned for such radiotherapy during the study period.
9. Investigator site personnel directly affiliated with this study and/or their immediate families; immediate family is defined as a spouse, parent, child, or sibling.
10. Cochlear employees or employees of Contract Research Organisations or contractors engaged by Cochlear for the purposes of this investigation.
11. Currently participating, or participated within the last 30 days, in another interventional clinical investigation involving an investigational drug or device.

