7.4.2 Concomitant Medication and Therapies

All medications and treatments given, whether or not to treat AEs/ADEs, must be recorded in the appropriate section of the CRF.

Prohibited therapies are the following:

- long-term systemic use of corticosteroids

- ototoxic drugs
- radiotherapy in the area of implantation

If a subject receives a prohibited therapy each situation will be evaluated case by case and judged by the responsible investigator.

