9.10.4 Concomitant medication

Concomitant medications will be defined as start or end date from surgery to end of study and will be presented by listings.

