#### **3.7.2 List of tables**

Table	Title
Table 14.1.1	Patient Disposition and Data Sets Analysed
Table 14.1.2	Protocol Deviations Leading to Exclusion from PP Population (ITT Population)
Table 14.1.2.1	Audiogram at screening - SSD patients (Safety Population)
Table 14.1.2.5	Audiogram at screening - mixed/conductive patients (Safety Population)
Table 14.1.3.1	Demographics and Baseline Characteristics (ITT Population)
Table 14.1.3.2	Demographics and Baseline Characteristics (PP Population)
Table 14.1.4.1	Device and hearing history (ITT Population)
Table 14.1.4.2	Device and hearing history (PP Population)
Table 14.1.6	Medical History (ITT Population)
Table 14.1.7	Surgical History (ITT Population)
Table 14.1.8.1	Prior Medications (ITT population)
Table 14.1.8.2	Concomitant Medications (ITT population)
Table 14.1.9	Listing of Concomitant Treatments/Procedures (ITT population)
Table 14.2.1.1	Threshold Audiometry - Free field Osia System vs Unaided (ITT Population)
Table 14.2.1.2	Threshold Audiometry - Free field Osia System vs Unaided (PP Population)
Table 14.2.1.3	Threshold Audiometry - Free field Osia System vs Unaided (landscape layout) (All patients - ITT Population)
Table 14.2.1.4	Threshold Audiometry - Free field Osia System vs Unaided (landscape layout) (Mixed/Conductive patients - ITT Population)
Table 14.2.1.5	Threshold Audiometry - Free field Osia System vs Unaided (landscape layout) (SSD patients - ITT Population)
Table 14.2.1.6	Threshold Audiometry - Free field Osia System vs Unaided by Site (ITT Population)
Table 14.2.1.7	Threshold Audiometry - Free field (PTA-4) Osia System vs Unaided by Site (ITT Population)
Table 14.2.2.1	Adaptive speech recognition in noise and Speech in quiet Osia System vs Unaided (ITT Population)

Table 14.2.2.2	Adaptive speech recognition in noise and Speech in quiet Osia System vs Unaided (PP Population)
Table 14.2.2.3	Adaptive speech recognition in noise and Speech in quiet Osia System vs Unaided (landscape layout) (All patients - ITT Population)
Table 14.2.2.4	Adaptive speech recognition in noise and Speech in quiet Osia System vs Unaided (landscape layout) (Mixed/Conductive patients - ITT Population)
Table 14.2.2.5	Adaptive speech recognition in noise and Speech in quiet Osia System vs Unaided (landscape layout) (SSD patients - ITT Population)
Table 14.2.2.6	Adaptive speech recognition in noise and Speech in quiet Osia System vs Unaided by Site (ITT Population)

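### The concomitant-medication definition leaves out a medicine started before surgery and still ongoing at study end, unless open end dates are closed at the last visit

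*SAP*

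**What the plan says.** Protocol 9.10.4 and SAP 3.4.4.16 share one definition. The SAP has "Concomitant medications will be defined as start or end date from surgery to end of study and will be presented by listings". The protocol has "Concomitant medications will be defined as start or end date from surgery to end of study" and likewise presents the result by listings. SAP 3.7.2 plans Table 14.1.8.1 for prior medications and Table 14.1.8.2 for concomitant medications, but the SAP does not define 'prior'.

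The data behind the listing are collected broadly. Protocol 7.4.2 says: "All medications and treatments given, whether or not to treat AEs/ADEs, must be recorded in the appropriate section of the CRF". The schedule of events collects concomitant therapies at every visit from screening to 6 months. Protocol 7.3.1 records current medication at screening and baseline, and SAP 3.4.4.3 presents it descriptively under medical history.

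The safety objective, in the synopsis and in the table under Protocol 6.2, names concomitant medication as a safety outcome, with information collected from surgery onwards. Neither document adds a clause for ongoing medicines or says that an open end date is set to the last visit.

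**The concern.** A definition of concomitant use should pick up any medicine taken during the observation period. This one asks instead whether a start or a stop occurred in that period. The two questions differ for long-running medicines. A drug begun before implantation and never stopped has no start or stop between surgery and the final visit, so it fails the test even though the subject took it on every study day.

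What is at stake is a listing for a named safety outcome. Someone reading it beside the healing, numbness and adverse-event data would see the short courses but not the unchanged long-term medication. The gap comes from the stated rule, not from missing data. A programmer who quietly used overlap logic instead would depart from the SAP, and SAP section 1 requires any such departure to be disclosed in the clinical investigation report.

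**Working it through.** The plan gives no figure on this point, so there is none to reproduce. The check applies the rule literally to each possible start/end pattern and compares it with actual use in the period.

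**Inputs.** Let S be surgery and E the end of study. For illustration, S = day 0 and E = day 182 (26 weeks × 7 days, for the 6-month visit in the schedule of events). Let s be the medicine's start day and e its end day. The example days below are arbitrary; only their order relative to S and E matters.

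**Rule as written** (Protocol 9.10.4, SAP 3.4.4.16): listed if S ≤ s ≤ E, or if an end date exists and S ≤ e ≤ E.

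**Actual use in the period:** s ≤ E, and either there is no end date or e ≥ S.

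| Pattern | s | e | Listed by the rule | Used in study |
|---|---|---|---|---|
| Started and ended before surgery | -100 | -10 | no | no |
| Started before, ended in study | -100 | 50 | yes | yes |
| Started and ended in study | 20 | 50 | yes | yes |
| Started in study, ongoing | 20 | none | yes | yes |
| Started before surgery, ongoing | -100 | none | **no** | **yes** |
| Started before surgery, ended after study | -100 | 300 | **no** | **yes** |
| Started after study end | 200 | none | no | no |

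Five patterns involve use during the study. The rule captures 3 and misses 5 − 3 = 2. Both missed patterns are continuous use from before surgery to beyond the last visit. At the last visit they look the same, because the medicine is simply still being taken. The overlap condition captures all five and still leaves out the two patterns with no use in the study.

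**If open end dates were closed at the last visit.** The ongoing record then has e = 182. Since 0 ≤ 182 ≤ 182, the literal rule lists it. The omission therefore depends on how open end dates are coded, which neither document states.

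**The 3-month report.** SAP 3.5.1 makes the first report, the primary analysis, from data up to 3 months. Take the cut as day 91 (13 weeks × 7 days). A medicine with s = -100 and e = 120 has no date in days 0 to 91, so the rule omits it from that report. The overlap condition keeps it, because -100 ≤ 91 and 120 ≥ 0. By the final report the rule lists it, because 0 ≤ 120 ≤ 182. A corrected definition should therefore name the data cut as well as the end of study.

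**The case against.** The strongest reply is that the sentence is shorthand and that little depends on it. Four parts of that reply deserve weight.

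- **Coding of ongoing records.** If the database closes open records at the last visit, nothing is lost. This stands as a condition on the finding. It does not remove the point, because neither document specifies that coding.
- **Baseline use is visible elsewhere.** Current medication is recorded at screening and presented under SAP 3.4.4.3, and Table 14.1.8.1 may also carry it. This largely stands. What those outputs do not show is that use continued after implantation.
- **Prohibited therapies.** A reader might infer that the rule hides long-term prohibited treatment, since Protocol 7.4.2 prohibits "long-term systemic use of corticosteroids" along with ototoxic drugs and radiotherapy in the implant area. The documents do not support that as a general consequence. Prohibited therapy begun after surgery has its start date in the window and is listed. Use already under way at entry is addressed by exclusion criteria 2, 5 and 8 in Protocol 7.2.2. Some could remain, because criterion 5 ("Use of ototoxic drugs that could be harmful to the hearing, as judged by the investigator") and part of criterion 2 rest on judgement, but the route is narrow.
- **PP membership.** A reader might also infer that the listing decides who is a protocol violator. No section says so. Protocol 7.4.2 has its own route: "If a subject receives a prohibited therapy each situation will be evaluated case by case and judged by the responsible investigator". Deviations are documented in the eCRF (Protocol 13) and listed separately (SAP 3.4.4.1), and the analysis sets are settled at the clean file meeting (Protocol 9.5, SAP 3.3). A subject wrongly included at entry is a separate ground for removal from the PP set.

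It would also be tempting to say that 100% of continuously used medicines are omitted. That figure is circular, because the class is defined as whatever the rule misses, and it assumes that ongoing records carry no end date in the window.

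**Conclusion.** The point holds as a minor reporting defect. Followed as written, the shared definition omits a medicine started before surgery and still ongoing at study end, and no other section repairs it. The conclusion assumes only that open end dates are not closed at the last visit, a step that neither document states.

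In terms of patterns, two of the five types of in-study use are missed. In terms of people, the documents give no data on long-term medication, so the number could be anything from none to all of the 30 planned subjects. No data are lost, since every medicine must be in the CRF. No test, estimate or power figure uses the listing. The harm is an incomplete listing for a named safety outcome, with a slightly wider gap at the 3-month report.

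**What to change.** In Protocol 9.10.4 and SAP 3.4.4.16, define a concomitant medication as one that started on or before end of study (or on or before the data cut, for the 3-month report) and was either ongoing or ended on or after surgery. Apply the same condition to Table 14.1.8.2.

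This wording works however ongoing records are coded, so no separate rule for open end dates is needed. Restricting Table 14.1.8.1 to medicines stopped before surgery would be a layout choice and is not required to correct the error.

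The cost is one sentence in each document, one program condition and a longer listing. No new data collection is needed.

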### **3.5 Conduct of Statistical Analysis**

The statistical analyses will be performed at Statistiska konsultgruppen by personnel employed at Statistiska konsultgruppen under supervision of [REDACTED]. The analyses will be performed by using SAS 9.4 (or later).

#### **3.5.1 Timing of analyses**

The first reporting of analyses will be made when all patients have completed their 3 months visit of the data up to 3 months. This analysis is regarded as the primary analysis. At the end of the study, at 6 months, the second and final reporting of the study will be made including all data up to the 6 months visit including data prior to the 3 months visit (ie all data in the study).

### **3.6 Quality control on statistical analysis**

Each programmer is responsible to continuously during working with data generation programs and statistical programs

### **3.7 Presentation of data**

#### **3.7.1 General**

All data will be presented in summarized tables. The distribution of continuous variables as well as change in continuous variables will be given as n, mean, SD, SEM, Median, Min and Max and the distribution of dichotomous and categorical variables will be given as number and percentages. For continuous variables estimated mean and the 95% two-sided confidence interval (bootstrapped) for difference between groups will be presented. The hypotheses' p-values and the corresponding/accompanying estimated with a 95% Ci will be presented where applicable.

Selected variables will be presented in figures showing either box plots or mean (95% CI) over time on actual values and/or change. Audiogram data will be presented as traditional audiograms.

#### **3.7.2 List of tables**

Table	Title
Table 14.1.1	Patient Disposition and Data Sets Analysed
Table 14.1.2	Protocol Deviations Leading to Exclusion from PP Population (ITT Population)
Table 14.1.2.1	Audiogram at screening - SSD patients (Safety Population)
Table 14.1.2.5	Audiogram at screening - mixed/conductive patients (Safety Population)
Table 14.1.3.1	Demographics and Baseline Characteristics (ITT Population)
Table 14.1.3.2	Demographics and Baseline Characteristics (PP Population)
Table 14.1.4.1	Device and hearing history (ITT Population)
Table 14.1.4.2	Device and hearing history (PP Population)
Table 14.1.6	Medical History (ITT Population)
Table 14.1.7	Surgical History (ITT Population)
Table 14.1.8.1	Prior Medications (ITT population)
Table 14.1.8.2	Concomitant Medications (ITT population)
Table 14.1.9	Listing of Concomitant Treatments/Procedures (ITT population)
Table 14.2.1.1	Threshold Audiometry - Free field Osia System vs Unaided (ITT Population)
Table 14.2.1.2	Threshold Audiometry - Free field Osia System vs Unaided (PP Population)
Table 14.2.1.3	Threshold Audiometry - Free field Osia System vs Unaided (landscape layout) (All patients - ITT Population)
Table 14.2.1.4	Threshold Audiometry - Free field Osia System vs Unaided (landscape layout) (Mixed/Conductive patients - ITT Population)
Table 14.2.1.5	Threshold Audiometry - Free field Osia System vs Unaided (landscape layout) (SSD patients - ITT Population)
Table 14.2.1.6	Threshold Audiometry - Free field Osia System vs Unaided by Site (ITT Population)
Table 14.2.1.7	Threshold Audiometry - Free field (PTA-4) Osia System vs Unaided by Site (ITT Population)
Table 14.2.2.1	Adaptive speech recognition in noise and Speech in quiet Osia System vs Unaided (ITT Population)

Table 14.2.2.2	Adaptive speech recognition in noise and Speech in quiet Osia System vs Unaided (PP Population)
Table 14.2.2.3	Adaptive speech recognition in noise and Speech in quiet Osia System vs Unaided (landscape layout) (All patients - ITT Population)
Table 14.2.2.4	Adaptive speech recognition in noise and Speech in quiet Osia System vs Unaided (landscape layout) (Mixed/Conductive patients - ITT Population)
Table 14.2.2.5	Adaptive speech recognition in noise and Speech in quiet Osia System vs Unaided (landscape layout) (SSD patients - ITT Population)
Table 14.2.2.6	Adaptive speech recognition in noise and Speech in quiet Osia System vs Unaided by Site (ITT Population)
Table 14.2.2.7	Listing of information regarding current hearing aid (ITT Population)
Table 14.2.3.1	BC Direct (ITT Population)
Table 14.2.3.2	BC Direct (PP Population)
Table 14.2.3.3	BC Direct (landscape layout) (ITT Population)
Table 14.2.3.4	BC Direct (landscape layout) (Mixed/Conductive patients - ITT Population)
Table 14.2.3.5	BC Direct (landscape layout) (SSD patients - ITT Population)
Table 14.2.4.1	HUI (ITT Population)
Table 14.2.4.2	HUI (PP Population)
Table 14.2.4.3	HUI (landscape layout) (ITT Population)
Table 14.2.4.4	HUI (landscape layout) (Mixed/Conductive patients - ITT Population)
Table 14.2.4.5	HUI (landscape layout) (SSD patients - ITT Population)
Table 14.2.5.1	APHAB (ITT Population)
Table 14.2.5.2	APHAB (PP Population)
Table 14.2.5.3	APHAB (ITT Population) (landscape layout) (ITT Population)
Table 14.2.5.4	APHAB (ITT Population) (landscape layout) (Mixed/Conductive patients - ITT Population)
Table 14.2.5.5	APHAB (ITT Population) (landscape layout) (SSD patients - ITT Population)
Table 14.2.6.1	The Speech, Spatial and Qualities of Hearing Scale (SSQ) (ITT Population)
Table 14.2.6.2	The Speech, Spatial and Qualities of Hearing Scale (SSQ) (PP Population)
Table 14.2.6.3	The Speech, Spatial and Qualities of Hearing Scale (SSQ) (landscape layout) (ITT Population)
Table 14.2.6.4	The Speech, Spatial and Qualities of Hearing Scale (SSQ) (landscape layout) (Mixed/Conductive patients - ITT Population)
Table 14.2.6.5	The Speech, Spatial and Qualities of Hearing Scale (SSQ) (landscape layout) (SSD patients - ITT Population)
Table 14.2.7.1	Surgery (ITT population)
Table 14.2.7.2	Surgery (PP population)
Table 14.2.8.1	Usability (ITT population)
Table 14.2.8.2	Usability (PP population)
Table 14.2.10.1	Coil-to-coil measurement (ITT population)
Table 14.2.10.2	Coil-to-coil measurement (PP population)
Table 14.2.10.1	Threshold Audiometry - Free field Osia System vs Softband (ITT Population)
Table 14.2.10.2	Threshold Audiometry - Free field Osia System vs Softband (PP Population)
Table 14.2.10.3	Threshold Audiometry - Free field Osia System vs Softband (landscape layout) (All patients - ITT Population)
Table 14.2.10.4	Threshold Audiometry - Free field Osia System vs Softband (landscape layout) (Mixed/Conductive patients - ITT Population)
Table 14.2.10.5	Threshold Audiometry - Free field Osia System vs Softband (landscape layout) (SSD patients - ITT Population)

Table 14.2.11.1	Adaptive speech recognition in noise and Speech in quiet Osia System vs Softband (ITT Population)
Table 14.2.11.2	Adaptive speech recognition in noise and Speech in quiet Osia System vs Softband (PP Population)
Table 14.2.11.3	Adaptive speech recognition in noise and Speech in quiet Osia System vs Softband (landscape layout) (All patients - ITT Population)
Table 14.2.11.4	Adaptive speech recognition in noise and Speech in quiet Osia System vs Softband (landscape layout) (Mixed/Conductive patients - ITT Population)
Table 14.2.11.5	Adaptive speech recognition in noise and Speech in quiet Osia System vs Softband (landscape layout) (SSD patients - ITT Population)
Table 14.3.1.1	Summary of Adverse Events (Safety Population)
Table 14.3.1.2	Adverse Events (AE), by CTCAE SOC and CTCAE Term (Safety Population)
Table 14.3.1.3	Adverse Device Events (ADE possibly, probably and definitely related), by CTCAE SOC and CTCAE Term (Safety Population)
Table 14.3.1.4	Serious Adverse Events (SAE), by CTCAE SOC and CTCAE Term (Safety Population)
Table 14.3.1.6	Adverse Events of Special Interest (AESI), by CTCAE SOC and CTCAE Term (Safety Population)
Table 14.3.2	Numbness (Safety Population)
Table 14.3.3.1	Device deficiency per visit (Safety Population)
Table 14.3.3.2	Device deficiency (number of events and subjects) (Safety Population)

